9.2.2. Exclusion Criteria

Patients meeting any of the following criteria will not be included in the study:

- Had medical claims indicating a diagnosis or procedure of rheumatic mitral valvular heart disease, heart valve replacement/transplant, venous thromboembolism, or transient AF 6 months prior to or on the index date.
- Had hip/knee replacement surgery within 6 weeks prior to or on the index date.
- Were pregnant during the study period.
- Had an OAC prescription during the 6 months pre-index date.
- Had follow-up time equal to 0 days.
- Had more than one OAC on the index date.

Flag: A flag will be created to evaluate the mechanical heart valve/mitral stenosis during the 6 months prior to or on the index date using narrow definition.

All codes for the selection criteria are detailed in Appendix [Table 4](#).

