17. ANNEX 2. ADDITIONAL INFORMATION

17.1. Appendix

Table 4. Exclusion Criteria

Diagnosis	ICD-9 Code	ICD-10 Code
Valvular Heart Disease	394.0, 394.1, 394.2, 394.9, 396.0, 396.1, 396.8, 396.9, 424.0, 745.xx	I050, I051, I052, I058, I059, I080, I088, I089, I340, I341, I342, I348, I349, Q213, Z952, Z953, Z954
Mechanical Heart Valve/ Mitral Stenosis (narrow definition)	ICD-9-CM: 996.02, 996.71, 394.0, 394.2, 396.0, 396.1, 746.5 ICD-9 procedure: 35.20, 35.22, 35.24, 36.23, 35.97 CPT: 33405, 92987, 33427, 33426, 33425, 33422, 33420, 33430	ICD- 10 diagnosis codes: T82.01XA, T82.02XA, T82.03XA, T82.09XA, T82.817A- T82.897A, T82.9XXA, I05.0, I05.2, I08.0, Q23.2 ICD-10 Procedure Codes: 02RF07Z, 02RF08Z, 02RF0JZ, 02RF0KZ, 02RF37H, 02RF37Z, 02RF38H, 02RF38Z, 02RF3JH, 02RF3JZ, 02RF3KH, 02RF3KZ, 02RF47Z, 02RF48Z, 02RF4JZ, 02RF4KZ, 02RG07Z, 02RG08Z, 02RG0JZ, 02RG0KZ, 02RG37H, 02RG37Z, 02RG38H, 02RG38Z, 02RG3JH, 02RG3JZ, 02RG3KH, 02RG3KZ, 02RG47Z, 02RG48Z, 02RG4JZ, 02RG4KZ, 02RH07Z, 02RH08Z, 02RH0JZ, 02RH0KZ, 02RH37H, 02RH37Z, 02RH38H, 02RH38Z, 02RH3JH, 02RH3JZ, 02RH3KH, 02RH3KZ, 02RH47Z, 02RH48Z, 02RH4JZ, 02RH4KZ, 02RJ07Z, 02RJ08Z, 02RJ0JZ, 02RJ0KZ, 02RJ47Z, 02RJ48Z, 02RJ4JZ, 02RJ4KZ, 02UG3JZ, X2RF03Z, X2RF33Z, X2RF43Z

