Valve Replacement Procedure	ICD-9-PCS/HCPCS Codes: 35.05-35.09, 35.20-35.28, 35.97	ICD-10-PCS Codes: 02RF07Z, 02RF08Z, 02RF0JZ, 02RF0KZ, 02RF37H, 02RF37Z, 02RF38H, 02RF38Z, 02RF3JH, 02RF3JZ, 02RF3KH, 02RF3KZ, 02RF47Z, 02RF48Z, 02RF4JZ, 02RF4KZ, 02RG07Z, 02RG08Z, 02RG0JZ, 02RG0KZ, 02RG37H, 02RG37Z, 02RG38H, 02RG38Z, 02RG3JH, 02RG3JZ, 02RG3KH, 02RG3KZ, 02RG47Z, 02RG48Z, 02RG4JZ, 02RG4KZ, 02RH07Z, 02RH08Z, 02RH0JZ, 02RH0KZ, 02RH37H, 02RH37Z, 02RH38H, 02RH38Z, 02RH3JH, 02RH3JZ, 02RH3KH, 02RH3KZ, 02RH47Z, 02RH48Z, 02RH4JZ, 02RH4KZ, 02RJ07Z, 02RJ08Z, 02RJ0JZ, 02RJ0KZ, 02RJ47Z, 02RJ48Z, 02RJ4JZ, 02RJ4KZ, 02UG3JZ, X2RF032, X2RF332, X2RF432
Hip/knee replacement surgery	ICD-9-PCS/HCPCS Codes: 81.40, 81.51, 81.52, 81.53, 81.54, 81.55	ICD-10-PCS Codes: 0SQ90ZZ, 0SQ93ZZ, 0SQ94ZZ, 0SQ9XZZ, 0SQB0ZZ, 0SQB3ZZ, 0SQB4ZZ, 0SQBXZZ, 0SR90J9, 0SR90JA, 0SR90JZ, 0SRB0J9, 0SRB0JA, 0SRB0JZ, 0SRA009, 0SRA00A, 0SRA00Z, 0SRA019, 0SRA01A, 0SRA01Z, 0SRA039, 0SRA03A, 0SRA03Z, 0SRA07Z, 0SRA0J9, 0SRA0JA, 0SRA0JZ, 0SRA0KZ, 0SRE009, 0SRE00A, 0SRE00Z, 0SRE019, 0SRE01A, 0SRE01Z, 0SRE039, 0SRE03A, 0SRE03Z, 0SRE07Z, 0SRE0J9, 0SRE0JA, 0SRE0JZ, 0SRE0KZ, 0SRR019, 0SRR01A, 0SRR01Z, 0SRR039, 0SRR03A, 0SRR03Z, 0SRR07Z, 0SRR0J9, 0SRR0JA, 0SRR0JZ, 0SRR0KZ, 0SRS019, 0SRS01A, 0SRS01Z, 0SRS039, 0SRS03A, 0SRS03Z, 0SRS07Z, 0SRS0J9, 0SRS0JA, 0SRS0JZ, 0SRS0KZ, 0SW90JZ, 0SW93JZ, 0SW94JZ, 0SWA0JZ, 0SWA3JZ, 0SWA4JZ, 0SWB0JZ, 0SWB3JZ, 0SWB4JZ, 0SWE0JZ, 0SWE3JZ, 0SWE4JZ, 0SWR0JZ, 0SWR3JZ, 0SWR4JZ, 0SWS0JZ, 0SWS3JZ, 0SWS4JZ, 0SRC07Z, 0SRC0JZ, 0SRC0KZ, 0SRC0LZ, 0SRD07Z, 0SRD0JZ, 0SRD0KZ, 0SRD0LZ, 0SRT07Z, 0SRT0JZ, 0SRT0KZ, 0SRU07Z, 0SRU0JZ, 0SRU0KZ, 0SRV07Z, 0SRV0JZ, 0SRV0KZ, 0SRW07Z, 0SRW0JZ, 0SRW0KZ, 0SWC0JC, 0SWC0JZ, 0SWC3JC, 0SWC3JZ, 0SWC4JC, 0SWC4JZ, 0SWD0JC, 0SWD0JZ, 0SWD3JC, 0SWD3JZ, 0SWD4JC, 0SWD4JZ, 0SWT0JZ, 0SWT3JZ, 0SWT4JZ, 0SWU0JZ,

Diagnosis	ICD-9 Code	ICD-10 Code
		0SWU3JZ, 0SWU4JZ, 0SWV0JZ, 0SWV3JZ, 0SWV4JZ, 0SWW0JZ, 0SWW3JZ, 0SWW4JZ

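### Some codes in the plan's own mechanical valve/mitral stenosis definition are only flagged and appear in no other valve exclusion row, so a residual group of valvular patients can stay in the NVAF cohorts

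*Combined protocol and SAP*

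**What the plan says.** Section 9.2.2 lists this exclusion: "Had medical claims indicating a diagnosis or procedure of rheumatic mitral valvular heart disease, heart valve replacement/transplant", among other conditions, in the 6 months up to and including the index date. After the bullets, under a separate label, it adds: "A flag will be created to evaluate the mechanical heart valve/mitral stenosis during the 6 months prior to or on the index date", using a narrow definition. It closes with "All codes for the selection criteria are detailed in Appendix" Table 4.

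That table (Section 17.1) is headed "Table 4. Exclusion Criteria". Three of its rows matter here:

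- **Valvular Heart Disease**: an exclusion row of diagnosis codes. Its ICD-10 column ends with the valve-status codes Z952, Z953 and Z954. Its ICD-9 column has no status code.
- **Valve Replacement Procedure**: an exclusion row. Its ICD-9 column reads "ICD-9-PCS/HCPCS Codes: 35.05-35.09, 35.20-35.28, 35.97", with no CPT or HCPCS code listed.
- **Mechanical Heart Valve/Mitral Stenosis (narrow definition)**: the row behind the flag. It includes "ICD-9-CM: 996.02, 996.71, 394.0, 394.2, 396.0, 396.1, 746.5", "ICD-9 procedure: 35.20, 35.22, 35.24, 36.23, 35.97", the CPT codes "33405, 92987, 33427, 33426, 33425, 33422, 33420, 33430", and ICD-10 diagnosis and procedure codes.

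The flag is not among the baseline variables of Table 1, and the visible text of Section 9.7 does not mention it.

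**The concern.** A narrow flag placed beside a broad exclusion should contain only codes that the exclusion already covers. If it contains others, the plan labels some patients as having a mechanical valve or mitral stenosis and still analyses them as non-valvular AF, which is the population the study is about.

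Such patients may have different stroke and bleeding risks. If they are spread unevenly between warfarin and apixaban, the comparison could shift. The status-code gap raises the same question by calendar time: with a 6-month look-back, a valve implanted years earlier leaves no procedure code in the window, so a status or complication code may be the only trace of it.

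**Working it through.** No stated figure has to be reproduced. The check is a set comparison: each entry of the narrow-definition row was looked up in the two valve exclusion rows, with code ranges in those rows expanded.

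| Narrow-row code type | Entries | In a valve exclusion row | Not in one |
|---|---|---|---|
| ICD-9 diagnosis | 7 | 4 | 3: 996.02, 996.71, 746.5 |
| ICD-9 procedure | 5 | 4 | 1: 36.23 |
| CPT | 8 | 0 | 8: 33405, 33420, 33422, 33425, 33426, 33427, 33430, 92987 |
| ICD-10 diagnosis | 10 | 3 | 7: T82.01XA, T82.02XA, T82.03XA, T82.09XA, the range T82.817A-T82.897A, T82.9XXA, Q23.2 |
| ICD-10 procedure | 60 | 57 | 3: X2RF03Z, X2RF33Z, X2RF43Z |
| **Total** | **90** | **68** | **22** |

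1. **Possible variants.** 36.23 resembles a code in the excluded range 35.20-35.28. The three X2RF codes ending in Z resemble X2RF032, X2RF332 and X2RF432 in the Valve Replacement row. If these four are typing or PDF-reading variants, 22 − 4 = 18 entries remain.
2. **Other rows.** Within the T82.817A-T82.897A range, T82817A and T82818A are caught by the VTE row. The other codes in the range are not.
3. **Status codes.** Z952-Z954 appear in the ICD-10 columns of the Valvular Heart Disease and Transient AF rows. Neither row has a status code in its ICD-9 column, although the plan uses ICD-9 V-codes elsewhere (V12.54 in Table 5, V45.86 in Table 9). The exclusion is therefore weaker in the ICD-9 part of the study period.
4. **Two readings of the narrow row.** If it is flag-only, as the 9.2.2 text suggests, patients with only an uncovered code stay in. If the table title makes it an exclusion, the flag is zero for every analysed patient and the 9.2.2 sentence has no purpose. The passages need reconciling either way.

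**Illustration of size (all inputs except 0.63 are assumed).** Let fW and fA be the shares of retained valve patients on warfarin and apixaban, and r their stroke/SE rate relative to other patients in the same arm. Treating the hazard ratio as a rate ratio and ignoring weighting:

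observed HR ≈ 0.63 × [1 + fA(r − 1)] / [1 + fW(r − 1)]

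The 0.63 is the obesity planning value in Section 9.5.

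- All on warfarin, fW = 1%, r = 1.5: 0.63 / 1.005 = 0.627.
- All on warfarin, fW = 3%, r = 3: 0.63 / 1.06 = 0.594.
- Equal shares in both arms: the factors cancel and the result is 0.63.
- All on apixaban, fA = 3%, r = 3: 0.63 × 1.06 = 0.668.

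The direction depends wholly on how the retained patients divide between the arms, which the documents do not report.

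**The case against.** The strongest reply is that the gap is much narrower than a first look suggests.

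- **A reader might infer that everyone meeting the narrow definition is merely flagged.** That is not so. Codes such as 394.0, 394.2, 396.0, 396.1, I05.0, I05.2, I08.0 and 57 of the 60 ICD-10 procedure codes are in exclusion rows. This stands, and it limits the point to the remaining entries.
- **The table title supports treating the row as an exclusion**, and 9.2.2 excludes valve replacement in words. This makes the plan ambiguous rather than plainly wrong. The separate flag sentence still favours the flag reading, and the code row that would carry out the worded exclusion lists no CPT code.
- **CPT-only patients may be few.** Section 9.4.1 describes VA inpatient procedure and surgery datasets, and Medicare inpatient claims with ICD procedure codes. Many valve operations would be caught there. This stands as a likely limit on numbers, but it does not cover the diagnosis codes or the missing ICD-9 status code. The HCPCS wording in the Valve Replacement heading proves little by itself, because the hip/knee row has the same heading and also lists no HCPCS code.
- **A reader might infer that the flag serves no analysis.** Section 9.7.2 contains redacted blocks, and Section 9.7.1 leaves the propensity variables to clinical judgement, so a use may exist. The supportable statement is that none is visible.
- **A reader might infer a bias in favour of apixaban.** That needs retained patients to be concentrated on warfarin and to have higher event rates. The documents give neither.

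**Conclusion.** The point holds as a residual gap and a text-to-table inconsistency. Of 90 narrow-definition entries, 18 to 22 are in neither valve exclusion row; the range depends on whether four entries are variants of listed codes. The ICD-9 side also lacks the valve-status exclusion that the ICD-10 side has. On the flag reading, a patient identified only by an uncovered code is kept as NVAF, apart from the two T82 codes that the VTE row removes.

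The number of such patients and the direction of any bias cannot be computed from the documents. The effect is probably small: with assumed shares of up to 3% in one arm and up to three times the event rate, a ratio of 0.63 moves to no further than 0.594 or 0.668. It is still worth correcting, because it decides who counts as non-valvular and the remedy is cheap.

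**What to change.** Reconcile 9.2.2 with Table 4 as follows:

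- Add the valve-specific codes to the exclusion rows: the eight discrete CPT codes (not a range, which could bring in unlisted codes); ICD-9 996.02, 996.71 and 746.5; ICD-10 T82.01XA, T82.02XA, T82.03XA, T82.09XA and Q23.2.
- Have a coder add an ICD-9 valve-status equivalent of Z952-Z954, check 36.23 and the X2RF variants, and leave out any code in T82.817A-T82.897A or T82.9XXA that is not valve-specific.
- Report the count removed by these additions, by arm and index year, in the attrition table.
- If any flag is kept, state in 9.2.2 what it covers and in 9.7 which analysis uses it.

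The cost is a sentence or two in 9.2.2 and 9.7, code-list edits, a coder's check, and the loss of what is probably a small number of patients.

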9.2.3. Cohorts

After applying the selection criteria, patients will be assigned to the following subgroups based on body weight and BMI measures:

1. Obese Patients: Patients with body mass index (BMI) ≥ 30 or body weight ≥ 100 kg within ± 6 months from the index date.
2. Non-Obese Patients: Patients not categorized as obese patients i.e. BMI < 30 or body weight < 100 kg patients within ± 6 months from the index date will be designated as non-obese patients.
3. Severely Obese Patients: Patients with BMI > 40 or body weight > 120 kg within ± 6 months from the index date.

4. **Non-Severely Obese Patients:** Patients not categorized as Severely Obese ie, BMI \leq 40 or body weight \leq 120 kg patients within \pm 6 months from the index date will be designated as non-severely obese patients.²⁴

For patients that have multiple body weights during \pm 6 months from the index date, the body weight closest to the index date will be used. Also, BMI will be given a preference over body weight in identifying patients into the above categories.

For each of the proceeding subgroup, patients will be categorized into the following cohorts based on their index OAC:

- a. Apixaban Cohort;
- b. Dabigatran Cohort;
- c. Edoxaban Cohort;
- d. Rivaroxaban Cohort;
- e. Warfarin Cohort.

The descriptive analysis will also be conducted separately among patients with low and standard dose OACs, defined below in [Section 9.3 Variables](#).

9.3. Variables

Baseline variables during the 6 months prior to, and on, the index date will be measured. Baseline variables will be evaluated using codes in any position unless noted otherwise.

Table 1. Baseline Demographic and Clinical Characteristic Variables

Variable	Data Source(s)	Operational Definition
Age	Both VA and Medicare	Age will be defined as of the index date and used to assign patients to age groups (eg, 18-54, 55-64, 65-74, 75-79, \geq 80 years).
Sex	Both VA and Medicare	A flag will be created for female beneficiaries and reported as a percentage.
US Geographic Region	Both VA and Medicare	The United States will be divided into 5 regions: Northeast, South, Midwest, West, and Other.
Race	Both VA and Medicare	Race will be identified and will be categorized as: White, Black, Other, and unknown.
Year of index OAC	Both VA and Medicare	A flag will be created for proportion of unique patients with index OAC identified in 2013, 2014, 2015, 2016, and 2017.

Variable	Data Source(s)	Operational Definition
Dose of Index DOAC	Both VA and Medicare	-Standard dose (apixaban 5 mg, dabigatran 150 mg, and rivaroxaban 20 mg) based on dose of the initial prescription of DOAC; -lower dose (apixaban 2.5 mg, dabigatran 75 mg, rivaroxaban 15 mg/10 mg) based on dose of the initial prescription of DOAC.
Body Weight	VA	Body weight will be obtained as continuous and categorical variables. The categories will be: ≤ 60 kg, 61-99 kg, 100-119 kg, and ≥ 120 kg. If a patient has multiple values, the value closest to the index date will be used.
BMI	VA	Body Mass Index: Body mass index will be calculated as weight in kilograms divided by the square of height in meters. Mean, median, and standard deviation will be provided for the continuous variable. The categories will be <18.5 , 18.5-24.9, 25-29.9, 30-39, and ≥ 40 . If a patient has multiple values, the value closest to the index date will be used.
Creatinine Clearance	VA	Creatinine Clearance: Creatinine clearance will be identified using LOINC codes (2160-0, 33914-3, 48642-3, 48643-1, 62238-1, 2164-2, 14682-9). A categorical variable for the glomerular filtration rate (GFR) will be created with the following cutoff points: <15 ml/min, 15-29 ml/min, 30-59 ml/min, 60-89 ml/min, and ≥ 90 ml/min. If a patient has multiple values, the value closest to the index date will be used. The creatinine clearance rate (CrCl) will be calculated based on serum creatinine for patients who only had serum creatinine information. ²⁵
INR	VA	International Normalized Ratio Test Results will be identified using Logical Observation Identifiers Names and Codes (LOINC; 34714-6, 38875-1, 46418-0, 52129-4, 5895-7, 5896-5, 61189-7, 6301-6, 72281-9) occurring anytime during the baseline period will be evaluated.
CHADS₂ Score	Both VA and Medicare	CHADS ₂ Score will be calculated according to the points algorithm outlined in Appendix Table 5 .

Variable	Data Source(s)	Operational Definition
CHA2DS₂-VASc Score	Both VA and Medicare	CHA2DS ₂ -VASc score will be calculated according to the points algorithm outlined in Appendix Table 6 .
HAS-BLED Score	Both VA and Medicare	HAS-BLED score will be calculated according to the points algorithm outlined in Appendix Table 7 .
Baseline Medication Use	Both VA and Medicare	A flag will be created for the following medications prescribed during the baseline period: angiotensin-converting enzyme inhibitors/ angiotensin-receptor blockers, aspirin, beta blockers, statins, proton pump inhibitors, H ₂ -receptor antagonists, antiplatelets, nonsteroidal anti-inflammatory drugs, inhibitors of warfarin, inducers of warfarin, dronedarone, digoxin, calcium channel blockers, renin angiotensin system antagonists, glucocorticoids, diuretics, metformin, sulfonylureas, thiazolidinedione, insulin, other diabetes drugs, antiulcer agents, and antidepressants (See Appendix Table 8 for codes).
Bariatric Surgery	Both VA and Medicare	A flag will be created for patients with claims for bariatric surgery (See Appendix Table 9 for codes).
CCI	Both VA and Medicare	Charlson Comorbidity index will be calculated as a continuous variable (See Appendix Table 10 for calculation and codes).
Comorbid Conditions	Both VA and Medicare	The following comorbid conditions will be flagged in baseline: History of stroke/SE, history of bleeding, myocardial infarction, renal disease, liver disease, dyspepsia or stomach discomfort, diabetes, hypertension, congestive heart failure, non-stroke/SE peripheral vascular disease, anemia and coagulation defects , transient ischemic attack, coronary artery disease, peripheral artery disease (See Appendix Table 11 for codes).

Table 2. Clinical and Outcome Variables

Variable	Data Source(s)	Operational Definition
Major Bleeding Event	Both VA and Medicare	Major bleeding event(s) observed during follow-up will be identified using hospital claims which had a MB diagnosis as the primary diagnosis code and occurring anytime during the follow-up period of drug use or within 30 days from the last day of supply of treatment prescription. A major bleeding event will be a dichotomous variable that equals 1 if there is ≥ 1 bleeding event during the follow-up period. Time to the first major bleeding event will be calculated. The first major bleeding event will be stratified by gastrointestinal (GI), intracranial hemorrhage (ICH), and other MB. (See Appendix Table 12 for codes).
Stroke/SE Event	Both VA and Medicare	Stroke/SE will be identified using hospital claims which had a stroke/SE diagnosis code as the primary diagnosis code and occurring anytime during the period of drug use or within 30 days from the last day of supply of treatment prescription. Stroke/SE will be a dichotomous variable that equals 1 if there is ≥ 1 stroke event during the follow-up period. Time to the first stroke/SE event will be calculated. The first stroke/SE event will be stratified by ischemic stroke, hemorrhagic stroke, and SE. (See Appendix Table 12 for codes).
Net Clinical Benefit	Both VA and Medicare	For patients with stroke/SE OR MB event, net clinical benefit will be assessed by evaluating the first hospital claim for a stroke/SE or MB event. The hospital claim can occur anytime during the period of drug use or within 30 days from the last day of supply of treatment prescription.
INR	VA	International Normalized Ratio Test Results will be identified using Logical Observation Identifiers Names and Codes (LOINC; 34714-6, 38875-1, 46418-0, 52129-4, 5895-7, 5896-5, 61189-7, 6301-6, 72281-9) occurring anytime during the period of drug use or within 30 days from the last day of supply of treatment prescription. The mean

Variable	Data Source(s)	Operational Definition
		and median number of INR tests for warfarin patients will be calculated. The distribution of INR values (mean, median, maximum, minimum, Q1, Q3) will be evaluated descriptively and flags will be created for INR <2, 2-3, and >3.
Time in Therapeutic Range (TTR)	VA	
TTR will be calculated using the Rosendaal method²⁶ and will be computed using INR values among warfarin patients during the follow-up. This method calculates INR-specific person-time by incorporating the frequency of INR measurements and their actual values, and assuming that changes between consecutive INR measurements are linear over time. TTR will be calculated based on the percentage of time a patient remained in therapeutic range evaluated during the entire follow-up period.
 
Flags will be created for TTR ≥65% [good] and TTR <65% [poor].

CCI [REDACTED]	[REDACTED]	[REDACTED]
CCI [REDACTED]	[REDACTED]	[REDACTED]

Variable	Data Source(s)	Operational Definition
CCI [REDACTED]	[REDACTED]	[REDACTED]

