7. RATIONALE AND BACKGROUND

Atrial fibrillation (AF) is recognized as the most common sustained cardiac arrhythmia in the United States and is associated with a near five-fold excess of stroke.¹ The prevalence of AF was estimated at 5.1 million in 2010 and projected to be 9.3 million in 2030 in the United States with an annual increase of 3.6%.² AF also bears substantial economic burden. The direct health care costs associated with AF were estimated at approximately \$6 billion annually.³

Vitamin K antagonists (VKAs; ie, warfarin) have been the mainstay treatment for stroke prevention among AF patients, reducing stroke by approximately 60%.⁴ Over the past 25 years, VKA use has been expanded from preventing stroke in valvular disease-associated AF patients to patients with non-valvular AF (NVAF).⁴

Warfarin therapy requires close monitoring of the international normalized ratio (INR). The INR range from 2.0 to 3.0 (therapeutic range) was proven to be efficient in stroke prevention among AF patients, and is recommended in the treatment of AF.^{5,6} However, due to its limited therapeutic index and possible drug and food interactions, only about half of AF patients in the United States receive warfarin therapy as recommended.⁷

Over the last several years, direct oral anticoagulants (DOACs), including apixaban, dabigatran, edoxaban, and rivaroxaban, were approved in the United States for stroke prevention among NVAF patients. Clinical trials demonstrated that DOAC use has shown stroke risk reduction similar or superior to warfarin, and lower or similar rates of bleeding.⁸⁻¹¹ In the years since their approval, DOACs have been increasingly preferred over warfarin due to

the convenience of fewer routine monitoring visits, no requirements for dose adjustment, and limited dietary interactions.

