9. RESEARCH METHODS

9.1. Study Design

9.1.1. Key Index Period Definitions

[figure not shown]
- **Study Period:** The study period will range from January 1, 2013 through December 31, 2017.
- **Patient Identification Period:** The identification period will range from July 1, 2013 until December 31, 2017, allowing for a 6-month baseline period prior to the index date.
- **Baseline Period:** The baseline period will be 6 months prior to, and on, the index date.
- **Follow-up Period:** The follow-up period will be defined as the time period between the day after the index date and end of study period (December 31, 2017). Patients will be followed from the day after the index date to 30 days after the date of discontinuation, switch, death, end of study period, or end of continuous medical enrollment (Parts A & B), whichever is earlier.

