9.2. Setting

Adult patients prescribed a DOAC or warfarin will be selected between July 1, 2013 and December 31, 2017. Patients will be required to have one or more AF diagnosis claim in any position before or on index date. Patients will be required to have health plan enrollment (Parts A and B) for 6 months prior to the index date to ensure availability of complete patient medical history.

Follow-up Period:

The follow-up period will be defined as the time period between the day after the index date and end of study period (December 31, 2017). Patients will be followed from the day after the index date to 30 days after the date of discontinuation, switch, death, end of study period, or end of continuous medical enrollment (Parts A & B), whichever is earlier.

To assess first stroke/SE event, patients will be censored at first stroke/SE occurring anytime during period on the drug or within 30 days from the last day of days' supply of treatment prescription, 30 days after date of discontinuation, switch, death, end of study or end of continuous medical enrollment (Parts A and B), whichever is earlier.

To assess first MB event, patients will be censored at first major bleeding occurring anytime during period on the drug or within 30 days from the last day of days' supply of treatment prescription, 30 days after date of discontinuation, switch, death, end of study or end of continuous medical enrollment (Parts A and B), whichever is earlier.

For patients with stroke/SE or MB event, net clinical benefit will be assessed by evaluating the first hospital claim for a stroke/SE or MB. The hospital claim can occur anytime during the period of drug use or within 30 days from the last day of supply of treatment prescription.

Other Factors Affecting Censoring During Follow-up

Discontinuation

Discontinuation will be defined as no evidence of index OAC prescription for 30 days from the last day of days' supply of last filled prescription. The date of discontinuation will be the last day of days' supply of last filled prescription. The follow-up will be censored at 30 days after the index drug discontinuation date.

Switch

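### For warfarin patients who stop, the INR and TTR windows run up to 30 days past the last day of supply, so Aim 4 can mix stopping with quality of control

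*Combined protocol and SAP*

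**What the plan says.** Four statements fix the window for a warfarin patient who discontinues.

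- **INR values** (Section 9.3, Table 2, INR row) are collected if "occurring anytime during the period of drug use or within 30 days from the last day of supply of treatment prescription". The stroke/SE row of the same table uses the same window.
- **TTR** (Section 9.3, Table 2, TTR row): "TTR will be calculated based on the percentage of time a patient remained in therapeutic range evaluated during the entire follow-up period". The abstract repeats this.
- **End of follow-up** (Section 9.1.1): "Patients will be followed from the day after the index date to 30 days after the date of discontinuation", unless another censoring event comes first. Section 9.2 agrees: "The follow-up will be censored at 30 days after the index drug discontinuation date".
- **Discontinuation date** (Section 9.2): "The date of discontinuation will be the last day of days' supply of last filled prescription". Discontinuation itself is "no evidence of index OAC prescription for 30 days from the last day of days' supply of last filled prescription", so it is judged from fills.

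TTR is computed by the Rosendaal method, "assuming that changes between consecutive INR measurements are linear over time". Table 2 flags INR as below 2, 2 to 3, or above 3, and TTR as good (at least 65%) or poor (below 65%). Aim 4 (Section 8.1.2) reports both distributions among obese and severely obese warfarin patients and compares baseline characteristics of the good and poor TTR groups. No visible text restricts INR values or TTR person-time to days covered by warfarin supply, and no visible sensitivity analysis does so.

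**The concern.** Sections 9.4 and 9.9 present INR and TTR as a view of how warfarin is managed. A 30-day tail is easy to understand for a clinical event. An INR drawn after a patient has stopped reflects the absence of warfarin, not how well it was controlled.

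Such a value acts in two ways. It is counted directly in the INR flags, most plausibly as below 2. It also becomes the end point of a Rosendaal segment, so days after supply ended are added to the TTR denominator and scored by the interpolated line. A patient whose control was good while on supply can then be flagged poor. The baseline comparison in Aim 4 would partly describe who stopped early rather than who was poorly controlled.

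A switch to a DOAC cannot shorten this tail. Section 9.1.2 gives warfarin as the index drug only to patients with no DOAC claim, so the tail is cut short only by death, end of study or end of enrolment.

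**Working it through.** The documents give no expected TTR and no share with good control, so there is no figure of the plan's own to reproduce.

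**Inputs from the documents:** therapeutic range 2.0 to 3.0 (Section 7); TTR cut-off 65% and linear interpolation (Table 2); tail of up to 30 days (Sections 9.1.1 and 9.2).

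**Assumptions:** T days on supply, all spanned by INRs, with an INR of 2.5 on the last day of supply; on-supply TTR p, shown mainly at 70%; tail INRs as stated. The documents do not say how time after the last INR is treated. I take it as not counted, since Rosendaal assigns time between measurements.

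**Case A: no INR in the tail.** No segment is added and TTR stays at 70.0% for every T.

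**Case B: one INR of 1.0 at day +30.** The line from 2.5 to 1.0 crosses 2.0 after 30 × (2.5 − 2.0)/(2.5 − 1.0) = 10 days, so 10 tail days are in range and 20 are out. TTR = (pT + 10)/(T + 30). For T = 90: (63 + 10)/120 = 60.8%.

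**Case C: INR 1.0 at days +7 and +30.** In-range tail days = 7 × 0.5/1.5 = 2.33. TTR = (pT + 2.33)/(T + 30). For T = 90: 65.33/120 = 54.4%.

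**Case D: INR 2.5 at day +30** (warfarin still being taken). All 30 days are in range. TTR = (pT + 30)/(T + 30). For T = 90: 93/120 = 77.5%.

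**Upper bound: all 30 tail days measured and out of range.** TTR = pT/(T + 30). For T = 90: 63/120 = 52.5%.

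Results for p = 70%:

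| Days on supply (T) | A | B | C | D | Upper bound |
|---|---|---|---|---|---|
| 90 | 70.0% | 60.8% | 54.4% | 77.5% | 52.5% |
| 180 | 70.0% | 64.8% | 61.1% | 74.3% | 60.0% |
| 365 | 70.0% | 67.2% | 65.3% | 72.3% | 64.7% |
| 730 | 70.0% | 68.6% | 67.5% | 71.2% | 67.2% |

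**Time on supply below which a good patient is flagged poor.**

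- Case B: set (pT + 10)/(T + 30) = 0.65, so T = 9.5/(p − 0.65). This gives 190 days at p = 70%, 95 at 75% and 63 at 80%.
- Upper bound: T = 19.5/(p − 0.65), which gives 390, 195 and 130 days.

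**Opposite direction.** An on-supply TTR of 60% with 30 in-range tail days becomes (0.6T + 30)/(T + 30): 70.0% at T = 90, 65.7% at 180 and 63.0% at 365. A poor patient can therefore be flagged good.

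**The case against.** The strongest reply is that nothing in the plan scores time after supply as out of range. That is correct. A reader might infer from the window alone that the whole 30 days counts as poor control and that discontinuers are systematically pushed below 65%. The documents do not support this. Under Rosendaal the tail contributes only if an INR is drawn in it, the early interpolated days may be in range, and Case D shows TTR rising. The upper-bound column needs INR to be out of range from the first day after supply ends as well as a late measurement in the tail. In Case B the thresholds are about half as long.

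A reader might also use the 55% warfarin loss in Section 9.5 to estimate how many patients are affected. Read as an annual stopping rate, it would give 1 − exp(−0.7985 × 195/365) = 35% stopping before 195 days, where 0.7985 = −ln(1 − 0.55). That does not hold. Section 9.5 does not call the figure annual and does not equate loss to follow-up with stopping warfarin; death and end of enrolment also end follow-up. Even a true stopping share would not be a reclassification rate, because it includes patients already below 65% and those with no INR in the tail.

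Third, the last day of supply is a proxy built from fills, and Section 9.9 itself cautions that a filled prescription does not show how the drug was taken. Cutting there removes some valid INRs from patients still taking tablets. This stands, and it is the reason to report both windows rather than replace one with the other. It does not remove the concern, since the planned window still pools values from patients who have and have not stopped.

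**Conclusion.** The point holds as a conditional one. For warfarin discontinuers, both windows extend up to 30 days past the date that the plan calls discontinuation. Where an INR is drawn there, Aim 4's INR flags and its good/poor TTR split can mix stopping with control. The patients most exposed have a short time on supply or a TTR close to 65%. In the illustration (INR 2.5 falling to 1.0 over 30 days), a 70% patient is flagged poor with less than 190 days on supply. Those still on supply at the end of follow-up are not affected.

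The net direction and the number reclassified cannot be computed: the documents give no frequency of INR testing after supply ends, no distribution of time on supply and no TTR distribution. In the visible text the effect stops at Aim 4, a secondary and descriptive aim in warfarin patients, and does not reach the apixaban versus warfarin comparison. Redacted analyses cannot be judged. This is a cheap improvement, not a threat to the main results.

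**What to change.** In Section 9.3, Table 2, compute the INR distribution, TTR and the 65% flags with the window ended at the discontinuation date (last day of supply). Report Aim 4 under this window and under the planned one, side by side. Leave the 30-day tail in place for stroke/SE, major bleeding and net clinical benefit.

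The cost is one sentence, one date cut-off in the code and a second set of Aim 4 columns. The truncated version loses some INRs from patients still taking leftover tablets; comparing the two sets of results would show how much that matters. Refill gaps of under 30 days during treatment would still count under either window, so the change reduces the mixing without removing it entirely.
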